4.4.7 Imputation of missing exposure end dates

Exposure end dates should be completed for the final study analysis. For any subjects with missing exposure end dates at the final analysis, the missing date will be imputed to the earliest of date of withdrawal from the study or death date. If none of these dates are available then the date of last patient last visit will be used. The imputed exposure end date will be stored in the exposure analysis dataset and an exposure end date imputation flag variable will be derived indicating which exposure end date records are imputed. Imputed exposure end dates will also

be stored on the study treatment end date variable (ADSL.TRTEDT). This variable will hold the last date of exposure across both study treatments.

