16.3 Follow-Up Assessments after Discontinuation of Study Treatment or Study Withdrawal

If study treatment is permanently discontinued **without** disease progression:

- the subject will complete the Post-Treatment Follow-Up Visit (see Time and Events Table) within 28 days (+7 days) after last dose of study treatment and prior to starting a new anti-cancer treatment or treatment with an investigational agent.
- the subject will continue to have disease assessments performed every 12 weeks until disease progression, initiation of a new anti-cancer treatment, or death, whichever comes first.

If study treatment is permanently discontinued **with** disease progression and/or subject is withdrawn from the study:

- The subject must make every effort to complete the Post-Treatment Follow-Up Visit (see Time and Events Table [Section 7.1]) within 28 days (+7 days) after last dose of study treatment and prior to starting any other anti-cancer treatment or treatment with an investigational agent.

All subjects permanently discontinuing study treatment will have a dermatologic exam performed monthly (± 7 days) for the first 6 months following discontinuation of study treatment. Subjects will be followed concurrently for survival and subsequent anti-cancer treatment every 3 months (± 14 days) until they die, withdraw consent, are lost to follow, or up to a time period that is dependent on the criteria defined in Section 16.4. When subjects are no longer required to be followed for survival, they will be notified accordingly.

If subjects are unable to attend clinic visits during survival follow-up, contact may be made via another form of communication (e.g., phone, mail, etc.).

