Adverse events, serious adverse events, death, laboratory data, vitals, ECG and ECHO, will be assigned to the study time periods defined below. Partial dates will be imputed into full dates, if applicable, for slotting data to the appropriate categories below (see Section 4.4). Flag variables (time in relation to study treatment) indicating the study time periods will be added to these datasets.

Pre-therapy is defined as the time prior to the subject's first dose of study treatment.

On-therapy is defined as the time from first dose of study treatment until 30 days after the last dose date of study treatment.

Post-therapy is defined as any time beyond the on-therapy period.

Some datasets include the first dose day as On-therapy and some exclude the first dose date as On-Therapy. The first dose day (Day 1) is considered pre-therapy for ECOG, ECG, vital signs, liver events, lab tests, and cardiac scan. The first dose day (Day 1) is considered to be On-therapy for adverse events and concomitant medications.

Study time period for concomitant medications and blood and blood supportive care products

Concomitant Medication and Blood and Blood Supportive Care Product start and end dates will be assigned to study time periods in relation to first dose of study treatment as defined below. The start date reference time flag variables and end date reference time flag variables will be added to the concomitant medications and blood and blood supportive products datasets, respectively.

Start relative to treatment: Assign to 'BEFORE' if start date is prior to study treatment start date or if subject has not taken any study treatment or (start date is missing and end date is before study treatment start date). Else assign to 'DURING' if the start date falls on or between the first and last dose dates of study treatment or if subject is ongoing (not all study treatment

discontinuation records completed) or start date is missing. Else assign to 'AFTER' if start date is after the on-therapy period.

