2.3.3 Study treatment / compliance

A summary of study treatment status will be provided for the ATS population. This display will show the number and percentage of subjects who are ongoing or discontinued study and the primary reason(s) for discontinuation of study treatment. Reasons for study treatment discontinuation will be presented in the order they are displayed in the eCRF. Separate tables will be produced for dabrafenib and trametinib. Separate listings for study treatment discontinuation will also be generated for dabrafenib and trametinib.

Summary of exposure to study treatment will be provided. The summary will include subject daily dose, population level daily dose, cumulative dose, duration on treatment for dabrafenib, duration on treatment for trametinib, and duration on combination treatment. The subject average daily dose is defined as the subject's cumulative dose divided by the duration on study

treatment. For the analysis of population level daily dose, a dose on each day for each subject will be treated as an observation and the summary will be based on the dose on each individual day for all subjects. Duration on treatment for dabrafenib or trametinib is defined as months from the first dose to the last non-zero dose, regardless of dose interruption before the last non-zero dose. In addition to mean, median, min and max, duration on dabrafenib, duration on trametinib and duration on combination treatment will also be summarized in the following categories: <3 months, 3-6 months, >6-9 months, >9-12 months, >12-24 months, >24-36 months, and >36 months.

Dose reductions will be summarised by number of reductions and reasons for reductions for dabrafenib and trametinib separately.

Dose interruptions will be summarised by number of interruptions and reasons for the interruptions for dabrafenib and trametinib separately.

A summary of overall compliance based on the exposure data will be produced separately for dabrafenib and trametinib for the ATS population. Percentage overall compliance will be summarized using the mean, standard deviation, minimum, median, and maximum. In addition, percentage overall compliance will be categorized and summarized by <80%, 80%-105%, and >105%.

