2.7.2 Deaths

All deaths will be summarized based on the number and percentage of subjects, by time of death (on-therapy and post-therapy) and the primary cause of death. On-therapy and post-therapy are defined in section 2.1.1. A supportive listing will be generated to provide subject-specific details for subject who died.

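### SAP 4.4.7 fills a missing exposure end date with study exit or death without first checking whether the subject had already stopped treatment

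*SAP*

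**What the plan says.** SAP 4.4.7 opens by expecting complete data: "Exposure end dates should be completed for the final study analysis". For any end date still missing, "the missing date will be imputed to the earliest of date of withdrawal from the study or death date". A last resort follows: "If none of these dates are available then the date of last patient last visit will be used". Imputed records carry a flag. The imputed date is also carried into ADSL.TRTEDT, which holds the last exposure date over both drugs.

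That date drives other definitions. SAP 2.1.1: "On-therapy is defined as the time from first dose of study treatment until 30 days after the last dose date of study treatment". SAP 2.7.2 tabulates deaths "by time of death (on-therapy and post-therapy) and the primary cause of death". SAP 2.3.3 measures treatment duration up to the last non-zero dose. Its compliance formula divides cumulative dose by the product of treatment duration and prescribed dose.

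Stopping treatment and leaving the study are separate events. After permanent discontinuation, Protocol 16.3 provides: "Subjects will be followed concurrently for survival and subsequent anti-cancer treatment every 3 months". This runs until death, withdrawn consent or loss to follow-up, subject to the end of the study. Protocol 16.4 defines study completion and study discontinuation by events of that kind.

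Records of stopping treatment exist. SAP 2.3.3: "Separate listings for study treatment discontinuation will also be generated for dabrafenib and trametinib". Protocol 6.5 puts treatment stop dates in the eCRF. Footnote 55 of the Time and Event Table sets the Follow-up Visit within 28 (+7) days of the last dose.

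**The concern.** The imputation order contains only dates on which a subject leaves the study, plus one study-wide closing date. It has no step for a subject known to have come off drug earlier. For that subject, the analysis treats survival follow-up as time on treatment.

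The quantities at stake are exposure duration, compliance or cumulative dose, and the split of deaths into on-therapy and post-therapy. The death split matters most to a reader of the safety results. A death from progression long after the last dose would be reported as occurring on therapy. Because ADSL.TRTEDT takes the later date over the two drugs, one missing end date on one drug is enough.

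**Working it through.** The plan states no figure to reproduce, so the check applies its date rules to example subjects. Let S be the actual last dose and D the death, both in months from first dose. S and D are assumptions; the rules come from SAP 2.1.1, 2.3.3, 2.7.2 and 4.4.7.

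**1. Classification of the death.** With the true date, the death is on-therapy only if it falls within 30 days of S. Under 4.4.7 the last-dose date is set to the death date. The test becomes D ≤ D + 30 days, which always holds. The interval since the real last dose no longer matters.

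**2. Exposure and compliance.** Excess exposure is D − S and the ratio is D/S. Suppose the full prescribed dose was taken up to S and no dose is added after it. Calculated compliance is then 100 × S/D.

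| S | D | Excess (months) | Ratio | Compliance | Death, true date | Death, SAP rule |
|---|---|---|---|---|---|---|
| 3 | 12 | 9 | 4 | 25.0% | post-therapy | on-therapy |
| 6 | 24 | 18 | 4 | 25.0% | post-therapy | on-therapy |
| 6 | 36 | 30 | 6 | 16.7% | post-therapy | on-therapy |
| 12 | 36 | 24 | 3 | 33.3% | post-therapy | on-therapy |

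If the last dose is instead carried forward to the imputed date, compliance is preserved but cumulative dose is inflated by the same 3- to 6-fold ratio. SAP 4.4.7 does not say which applies. A subject still on drug at death has S = D, so the excess is zero and the class is correct.

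**3. Sensitivity of the death count.** The Amendment 08 rationale in the protocol reports 47 deaths at 20-Nov-2017, 3 of them during treatment (3/47 = 6.4%); the other 44 (93.6%) were not. On that base:
- one affected subject gives 4/47 = 8.5%;
- two give 5/47 = 10.6%;
- five give 8/47 = 17.0%.

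This snapshot is neither the final count nor based on the 30-day window. It shows only that a small on-treatment count moves with a few records.

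**4. Mean exposure.** With k affected subjects, 18 excess months each (assumed) and 206 enrolled, the mean shift is 18k/206: 0.09 months for k = 1, 0.44 for k = 5 and 0.87 for k = 10. The size of the treated population, the proper denominator, is not given.

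**5. Who could be affected.** The Amendment 11 rationale reports 55 of 206 subjects on treatment at 06-Apr-2020, so 206 − 55 = 151 (73%) were not. A missing end date among subjects who had stopped and then stayed in follow-up would be imputed too late. This describes the pool at risk and says nothing about how many dates are missing.

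**The case against.** The strongest reply is that 4.4.7 is a flagged fallback for records that should not exist at the final analysis. It gives about the right answer for subjects on drug at death, lost while on drug, withdrawing from treatment and data collection together, or moved to other supply at closure. SAP 2.1.1 treats subjects without completed discontinuation records as ongoing, so an open end date may well belong to one of these groups. All of that stands, and it rules out the inference that every imputed date is wrong by the length of follow-up. It does not answer the narrower point, because 4.4.7 does not check which group the subject is in.

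A reader might also infer the following, which the documents do not support:

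- **Late adverse events become on-therapy in the same way as deaths.** Under Protocol 11.7, routine collection ends 30 days after discontinuation. Later reports are limited to related SAEs and events the investigator believes possibly related, so the effect is much smaller.
- **A missing end date in the middle of a dosing sequence would be set to death and double-count dose.** The section gives no instruction for intermediate records, so this is speculation.
- **The discontinuation form certainly holds a last-dose date.** Protocol 16.2 requires the reason to be documented, and the stop date named in Protocol 6.5 may be the missing field. The annotated eCRF is not among the documents.

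Protocol 4 also speaks of subjects being withdrawn from the study at progression. If sites recorded it that way, the error would be smaller for them. Protocol 16.3 and 16.4 point to the later date.

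**Conclusion.** The concern holds in a limited form. For a subject who stopped drug and then stayed in survival follow-up, the stated rule overstates exposure by the time from actual stop to death or study exit. It also distorts compliance or cumulative dose. When death is the imputed date, it always produces an on-therapy death. In the assumed cases, the overstatement is 9 to 30 months, or 3- to 6-fold.

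The trial-wide effect cannot be stated, because the number of missing dates is not in the documents. It may be small or nil, and the imputation flag makes affected records traceable. ORR is not directly affected, and the PFS and OS definitions do not use the exposure end date. This is a minor correction, worth making because the rule as written gives a wrong value where a tighter one is likely to be on record.

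**What to change.** Replace the order in SAP 4.4.7 with the following, applied to each drug:

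1. If the subject has a treatment discontinuation record for that drug, use the documented last-dose or discontinuation date where one is available.
2. If there is such a record but no usable date, use the earliest of the post-treatment Follow-up Visit, the last documented dispensing or dosing-diary date, death and study withdrawal.
3. Only if nothing shows that treatment had stopped, keep the current rule: the earlier of study withdrawal or death, otherwise last patient last visit.

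Report how many end dates were imputed. Step 2 is needed so that off-treatment subjects without a discontinuation date do not fall back to the study-exit rule.

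The cost is a few sentences in the SAP, a change to the exposure dataset program and one reported count. Whether the discontinuation form supplies a date should first be checked against the annotated eCRF.

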4.5 Multiple Assessments

All data will be reported according to the nominal visit date for which it was reported (that is, no visit windows will be applied during dataset creation). Unscheduled data will only be included in the display sections that report worst-case on-therapy.

If multiple assessments are reported on the same date for the same scheduled planned time, then the mean of multiple measurements reported for the same date will be analyzed, with the exception of laboratory data reported from both central and local laboratories. If laboratory data is reported from both central and local laboratories with the same date, then the central laboratory data will be analyzed to provide consistency with measurements from other subjects.

4.6 Laboratory parameters derivations

Reference ranges for all laboratory parameters collected throughout the study are provided by the laboratory. A laboratory value that is outside the reference range is considered either high abnormal (value above the upper limit of the reference range) or low abnormal (value below the lower limit of the reference range). Note: a high abnormal or low abnormal laboratory value is not necessarily of clinical concern. The laboratory reference ranges will be provided on the listings of laboratory data. Clinical laboratory test results outside of the reference range will be flagged in the listings.

To identify laboratory values of potential clinical importance, National Cancer Institute Common Terminology Criteria for Adverse Events (NCI-CTCAE v4.0) will be used to assign grades to the relevant laboratory parameters.

4.7 ECG parameters

To identify QTc (Bazett's and Fridericia's) values of potential clinical importance, NCI-CTCAE v4.0 will be used to assign grades (see adverse event 'Electrocardiogram QT corrected interval prolonged').

ECG Parameter	Potential Clinical Importance (PCI) Range	Unit
Absolute QTcB or QTcF interval	≥450 to <481 (Grade 1) ≥481 to <501 (Grade 2) ≥501 (Grade 3)	Msec
Increase from baseline	Increase of ≥31 to ≤60 Increase of >60	Msec

The following criteria will be used to flag other ECG values that are values of potential clinical importance:

ECG Parameter	Potential Clinical Importance (PCI) Range	Unit
PR interval	<110 (L) and >220 (H)	Msec
QRS interval	<75 (L) and >110 (H)	Msec

4.8 Cardiac Scan Modalities (ECHO)

An ECHO modality will be used for determining cardiac scan data (e.g., left ventricular ejection fraction (LVEF)) for all subjects throughout the study. The absolute change from baseline value will not be calculated for any time point in which the post-baseline value was determined by a cardiac scan modality other than ECHO.

4.9 Left ventricular ejection fraction

The following criteria will be used to flag LVEF values that are values of potential clinical importance:

To identify LVEF values of potential clinical importance, NCI-CTCAE v4.0 will be used to assign categories that align with the grades for ‘Ejection fraction decreased’.

LVEF Parameter	Unit	Potential Clinical Importance (PCI) Range
Absolute change from baseline LVEF	%	
 • No change or any increase • Any decrease 
 ○ >0-<10 decrease ○ 10-19 decrease ○ ≥20 decrease ○ ≥10 decrease and ≥ LLN ○ ≥10 decrease and below LLN ○ ≥20 decrease and ≥ LLN ○ ≥20 decrease and below LLN
Relative change from baseline LVEF	%	
 • ≥20 decrease and ≥ LLN • ≥20 decrease and below LLN

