8.1.1.2 Left Ventricular Ejection Fraction (LVEF) Stopping Criteria

Decreases of the LVEF have been observed in subjects receiving trametinib monotherapy and in combination with dabrafenib. Therefore, ECHOs must be performed to assess cardiac ejection fraction at regular intervals as outlined in the Time and Events Table (Section 7.1).

Echo assessment should be performed by the same operator throughout the study where possible. Copies of all ECHOs will be collected by the sponsor for review. Instructions for submission of ECHOs are provided in the SPM. Dose modification guidance and stopping criteria for LVEF decrease are provided in Table 13.

Table 13 Dose Modification Guidelines and Stopping Criteria for LVEF Decreases

Presentation	LVEF decrease (%) or CTCAE Grade	Action and Dose Modification
Asymptomatic	Absolute decrease of >10% in LVEF compared to baseline and ejection fraction below the institutional LLN	
 ● Interrupt study treatment and repeat ECHO within 2 weeks¹ ● Report as an AE If the LVEF recovers within 4 weeks (defined as LVEF ≥LLN and absolute decrease ≤10% compared to baseline) 
 ● Consult with the Medical Lead and request approval for restart ● Restart treatment with trametinib reduced dose by one dose level 
 ● Restart dabrafenib at previous dose level ● Repeat ECHO 2 , 4 , 8 and 12 weeks after re-start; continue in intervals of 12 weeks thereafter ● If LVEF does not recover within 4 weeks 
 ● Consult with cardiologist ● Permanently discontinue study treatment ● Repeat ECHO after 2, 4, 8, 12, and 16 weeks or until resolution 
 ● Consult with the Medical Lead
Symptomatic ²	Grade 3: resting LVEF 39 to 20% or >20% absolute reduction from baseline	
 ● Permanently discontinue study treatment ● Report as a SAE ● Consult with cardiologist
	Grade 4: resting LVEF <20%	
 ● Repeat ECHO after 2, 4, 8, 12, and 16 weeks or until resolution².

Abbreviations: AE, adverse event; CTCAE, Common Toxicity Criteria for Adverse Events; ECHO, echocardiogram; LLN, lower limit of normal; LVEF, left ventricular ejection fraction; SAE, serious adverse event

1. If ECHO does not show LVEF recovery after 2 weeks, repeat ECHO 2 weeks later.

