18.3.3.1.3 Other Safety Measures

The results of scheduled assessments of vital signs, 12-lead ECG, ECHO and ECOG performance status will be summarized. Summaries will include data from scheduled assessments only. All data will be reported according to the nominal visit date for which it was recorded; no visit windows will be applied. All data will be listed.

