2.7.4 Other safety data

2.7.4.1 ECG and cardiac imaging data

The results of scheduled assessments of ECG will be summarized. A summary of ECG findings will classify each result into “Normal”, “Abnormal, not clinically significant” or “Abnormal, clinically significant” as entered on the eCRF. Bazett’s and Fridericia’s corrections of QT values will be summarized using the categories in section 4.7 for both an increase in grade from baseline and the amount of increase. The summaries will display results by visit and for the worst case (largest increase) post-baseline.

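### The SAP's LVEF bands, said to align with CTCAE grades, use no resting LVEF value, so Grade 4 and a minority of Grade 3 values cannot be told apart from lesser falls, and SAP 2.7.4.1 specifies no LVEF summary

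*SAP*

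**What the plan says.** SAP 4.9 introduces its LVEF table with this statement: "To identify LVEF values of potential clinical importance, NCI-CTCAE v4.0 will be used to assign categories that align with the grades for" decreased ejection fraction. The table has two parameters. The first is "Absolute change from baseline LVEF": no change or increase, any decrease, a fall of more than 0 but under 10, 10-19, and ≥20, with the ≥10 and ≥20 falls also split at or above versus below LLN. The second is "Relative change from baseline LVEF": a fall of ≥20%, split the same way at LLN.

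Protocol section 8.1.1.2, Table 13, prints two of the grades in its symptomatic row. One reads "Grade 3: resting LVEF 39 to 20% or >20% absolute reduction from baseline". The other, Grade 4, is a resting LVEF below 20%. The asymptomatic row sets the interruption criterion: "Absolute decrease of >10% in LVEF compared to baseline", together with a value below the institutional LLN. Section 11.2 h uses the same criterion for a protocol-specific SAE.

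On outputs, protocol 18.3.3.1.3 says: "The results of scheduled assessments of vital signs, 12-lead ECG, ECHO and ECOG performance status will be summarized". SAP 2.7.4.1, whose heading covers both ECG and cardiac imaging, opens with "The results of scheduled assessments of ECG will be summarized" and describes nothing but ECG results. SAP section 3 declares no change to the protocol's analyses.

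**The concern.** A reader of the final report will take bands described as aligned with CTCAE grades to be a count by grade. They are not. Two patients with the same fall can have different grades, because the grade depends on where LVEF ends up as well as how far it fell.

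Decreased ejection fraction is a recognised harm of this combination. Protocol 1.4 gives 7% of combination subjects in two Phase III studies, and the protocol sets dedicated stopping criteria. The measured ECHO values are the one source on this harm that does not depend on an investigator recording and grading an event. If the SAP is followed as written, that source yields bands that do not reproduce the grades, and no results section names a table for them.

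**Working it through.** The plan states no figure to reproduce, so the check places LVEF pairs in both schemes.

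**Inputs**
- Grade 3: resting LVEF 39 to 20%, or a fall of more than 20 points. Grade 4: resting LVEF below 20% (protocol Table 13).
- SAP absolute bands: >0 to <10, 10-19, ≥20; ≥10 and ≥20 also split at LLN (SAP 4.9).
- Lowest eligible baseline: the institutional LLN, or 50% where none is defined (protocol Table 3, note 7).
- Assumptions: whole-number values, baselines from LLN to 80%, post-baseline values from 5% up, and LLN of 50% or 55% as a range.

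**Step 1: Grade 3 by resting value.** A value x between 20 and 39 from baseline b is Grade 3 whatever the fall. It enters the SAP's 10-19 band when b − x < 20, that is, x > b − 20.

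| Baseline b | Resting values in the 10-19 band | Count out of 20 |
|---|---|---|
| 50 | 31-39 | 9 |
| 52 | 33-39 | 7 |
| 55 | 36-39 | 4 |
| 58 | 39 | 1 |
| 59 or more | none | 0 |

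With LLN 50% there are 31 baselines × 20 values = 620 pairs, of which 9 + 8 + … + 1 = 45 are affected (45/620 = 7.3%). With LLN 55% there are 26 × 20 = 520 pairs, of which 4 + 3 + 2 + 1 = 10 are affected (10/520 = 1.9%). All the other resting-level Grade 3 pairs fall in the ≥20 and below LLN band.

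**Step 2: a matched pair.** 52 to 38 is a 14-point fall and Grade 3, because 38 is within 39 to 20. 55 to 41 is also a 14-point fall but is not Grade 3: 41 is above 39 and 14 does not exceed 20. With LLN 50% both are filed as 10-19 and as ≥10 and below LLN. The relative band does not separate them either: 14/52 = 26.9% and 14/55 = 25.5%, both ≥20% and below LLN.

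**Step 3: Grade 4.** From a baseline of at least 50%, the smallest fall that reaches a value below 20% is 50 − 19 = 31 points. Every Grade 4 pair therefore lands in the ≥20 and below LLN band: 31 × 15 = 465 of 465 with LLN 50%, and 26 × 15 = 390 of 390 with LLN 55%. Grade 3 falls share that band, such as 65 to 39, and so do exact 20-point falls that are not Grade 3, such as 60 to 40. No band isolates Grade 4.

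**Step 4: cut-offs.** With LLN 50%, 55 to 45 is an exact 10-point fall to below LLN. It enters the SAP's ≥10 and below LLN band but does not meet the protocol's >10 criterion. An exact 20-point fall such as 60 to 40 enters the SAP's ≥20 band but is not Grade 3 under the protocol's >20.

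**Step 5: outputs.** SAP 2.7.4.1 refers to section 4.7 for its ECG categories, and 2.7.4.2 refers to 4.10 for vital signs. No results section refers to 4.9. Sections 4.7 and 4.10 print grade labels beside their QTc and blood pressure bands; 4.9 prints none.

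**The case against.** The strongest reply is that severe LVEF falls have another reporting route. Adverse events are graded by CTCAE v4.0 and summarised by maximum grade (SAP 2.7.1). Cardiac events are of special interest and summarised by maximum grade, by cohort and overall (SAP 2.7.1.1). Falls of more than 10 points to below LLN are protocol-specific SAEs (protocol 11.2 h), symptomatic Grade 3 and 4 falls must be reported as SAEs, and AEs leading to interruption are tabulated. The SAP 4.9 bands are flags of potential clinical importance and not the sole count of graded events. This stands, and it means a reader should not infer that Grade 4 would go unreported. It does not repair the measured-LVEF display, because those tables rest on what investigators report.

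Three further inferences are tempting but unsupported:

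- **That no LVEF summary is planned.** Protocol 18.3.3.1.3 plans an ECHO summary and says all data will be listed. The SAP keeps change from baseline in cardiac assessments as a safety endpoint and says change from baseline will be presented for safety data. The gap is that the SAP does not specify the summary.
- **That Grade 3 falls in general are filed with lesser ones, or with Grade 2.** Most resting-level Grade 3 values fall in the ≥20 band. The documents do not define Grade 2, so falls that are not Grade 3 is as far as they go.
- **That the bands use change from baseline alone.** Six categories add the LLN condition on the post-baseline value, although that condition isolates neither grade.

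It is also fair that SAP 4.9 never says its ≥10 band represents the interruption criterion, and that the difference touches only exact 10-point falls.

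**Conclusion.** The point holds as a defect in safety reporting. SAP 4.9 claims alignment with grades that its bands cannot reproduce. Grade 4 is never separable. Grade 3 is misplaced only for resting values of 31-39% from baselines of 50-58%, which is 1.9% to 7.3% of resting-level Grade 3 pairs on the assumed grids. Those are shares of whole-number pairs and not of patients: the documents give no LVEF distribution for this trial, so the number of subjects affected cannot be stated. The grade definitions used are those printed in protocol Table 13.

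SAP 2.7.4.1 omits an LVEF summary that the protocol requires, while section 3 declares no change. The efficacy analyses are untouched. This is worth correcting before the final tables are produced, because the remaining graded evidence depends on investigator reporting.

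**What to change.** All changes below are to reporting; none alters a clinical rule.

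1. In SAP 4.9 add bands on the post-baseline resting LVEF value that match the grades printed in Table 13: 39 to 20% or a fall of more than 20 points, and below 20%. Keep the existing change bands as a second display.
2. Reconcile the SAP's ≥10 and ≥20 with the protocol's >10 and >20, so that the number of subjects meeting the protocol's LVEF criterion can be reported from measured values.
3. In SAP 2.7.4.1 add LVEF summaries by visit and for the worst post-baseline value, by cohort and overall, with a reference to 4.9.
4. Separately, the protocol must be reconciled with itself. Table 13 has the asymptomatic event reported as an AE, while section 11.2 h lists the same criterion as a protocol-specific SAE. Until this is settled, AE and SAE counts may not be comparable across sites.

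The cost of items 1 to 3 is SAP wording and one table programmed from ECHO data already collected, with no new assessments. Item 4 is a protocol clarification.
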